5.2. Handling of Study Interventions

5.2.1. Supported Self-Management (SSM) - Experimental Intervention

5.2.1.1. *Required Interventions*

The following are considered standard elements of the SSM intervention:

- Needs assessment and collaborative development of an individualized treatment plan. Includes review of BPS baseline measures, a brief physical examination that includes manual palpation and brief postural, strength, and mobility assessments; completion of a Wellbeing Wheel (based on risk factors and the BPS model) and self-evaluation of what it would take to engage in adaptive pain behaviors (COM-B Self-Evaluation Questionnaire V1). These will be re-assessed as needed. In addition, a "Self-Reliance Check In" will be completed at 6 weeks to initiate a conversation regarding release to self-care.

- Education will be provided through the communication of key evidence-based *information* about chronic pain, BRLP, BPS factors, and self-management to enhance patients' *knowledge*.⁴⁸
- Skill training will be provided as indicated in strategies and exercises directed towards enhancing *physical, psychological, and social self-management skills*. This includes physical exercises (e.g. postural, strength, stabilization and mobility exercises);^{20,31} psychological strategies (e.g. progressive muscle relaxation, relaxed breathing, guided imagery, pacing, relaxation, problem solving, and cognitive restructuring);^{66,92,93} and social strategies, including pleasant activity planning with a social focus, and communication techniques for navigating relationships (e.g. work, family, friends) to garner support for self-sufficiency. Specific BCTs used as part of skill training include *instructions, demonstrations, practice and rehearsal, self-monitoring and graded progressions*.^{55,56}
- Spinal manipulation therapies (SMT) are manual procedures applied by a practitioner to the lumbar and sacroiliac spinal regions. SMT has been shown to be effective in relieving symptoms and improving mobility.^{20,31,102,103} SMT will be applied as a “bridge therapy” as indicated, to support patients’ abilities to engage in the skill development described above.

SMT will include soft-tissue work (e.g. cross-fiber stretch, light friction massage, etc.), mobilization (low velocity, low-high amplitude passive movements) and manipulation (high velocity, low amplitude thrust)

- Enablement (by addressing barriers and facilitators) will also be applied as indicated to improve patients’ unhelpful beliefs about their capabilities to self-manage BRLP and overall wellbeing. Specific BCTs used as part of enablement include *emotional support provided by the provider, value-based goal setting, and problem solving*.^{55,56}
- Persuasion will be used as needed to influence patients BRLP beliefs, optimism, and motivation which are important for the adaptation of healthy pain coping behaviors. The following BCTs will be integrated into the intervention: *verbal persuasion, focus on past successes, and framing/reframing*.^{55,56}
- Resources and materials will be provided to support the patient and include a workbook and digital recordings (e.g. of the physical, psychological and social exercises and strategies described above).

5.2.1.2. Allowed Interventions

The following summarizes optional SSM elements (based on patient needs):

- Soft tissue techniques which include cross-fiber stretch, longitudinal stretch, direct pressure, and deep friction applied to soft tissue from the lower ribs to the gluteal folds.
- Lumbar neural mobilization
- Heat may be used to facilitate the delivery of SMT (up to 10 minutes)

5.2.1.3. Prohibited Intervention

SSM providers are prohibited from delivering:

- Education or exercise recommendations beyond the scope of the SSM intervention or what is described under concomitant interventions
- SMT to the neck, upper thoracic spine (above the sixth thoracic vertebrae), or extremity joints (e.g., hip joint)
- Instrument assisted SMT (e.g., activator)
- Passive modalities other than heat for facilitating SMT (e.g., TENS, ice)
- Recommendations to use mind-body practices not described in required or allowable SSM interventions (e.g. yoga, Tai Chi)
- Lumbar belts, strapping, taping, etc.
- Recommendation of bed rest

5.2.2. Medical Care (MC) - Comparison Intervention

5.2.2.1. Required Interventions

First or second-line medications for the management of chronic BRLP. Decisions regarding medication selection will be made collaboratively between the provider and patient after a discussion of risk/benefit profiles and preferences.

- First-line medications include nonsteroidal anti-inflammatory drugs (NSAIDs)
- Second-line medications include systemic corticosteroids, skeletal muscle relaxants, acetaminophen, benzodiazepines, antiseizure medications, lidocaine patches serotonin and norepinephrine reuptake inhibitors, tricyclic antidepressants, and weak opioids (e.g. Tramadol, Tylenol with Codeine) for participants unable to tolerate or unresponsive to first-line medications

5.2.2.2. Allowed Interventions

None

5.2.2.3. Prohibited Interventions

Medical providers are prohibited from recommending the following interventions:

- Medication(s) not listed as first- or second-line under required interventions
- Referral for physical therapy, manual treatment, cognitive behavioral therapy, or any treatments provided by a PT, DC, or psychologist.
- Referral for interventional procedures (e.g., epidural steroid injections, intramuscular and facet joint injections)
- Education or exercise recommendations beyond what is described under concomitant interventions

- Recommendations to use Mind-body practices (e.g., yoga, Tai Chi, meditation) or intervention elements described in the SSM protocol
- Lumbar belts, strapping, taping etc.
- Recommending bed rest

5.3. Concomitant Interventions

5.3.1. Required Interventions

All participants will receive basic standardized information regarding the generally favorable prognosis of chronic BRLP. We will provide patients with an updated version of the Back in Action book²⁰ in print and/or electronic formats. The Back in Action book:

- Encourages patients to engage in their normal activities as soon as possible, even if it causes some pain.
- Encourages general aerobic exercise like walking, swimming, bicycling.
- Provides a brief summary of the general causes of chronic BRLP and reassurance that the majority of cases do not require specialty care.
- Emphasizes the patient's role in facilitating their own recovery by providing some general recommendations for symptom management (e.g. changing positions frequently).

5.3.2. Allowed Interventions

- Participants will be allowed to use OTC medications as needed during the course of the study.
- Participants will be allowed to continue self-care practices (e.g., heat, ice, stretching) for chronic BRLP they used prior to the study.
- Participants assigned to SSM who experience a significant worsening of chronic BRLP symptoms that cannot be managed by the assigned and concomitant interventions will be referred to the study's medical care provider for a short-course of 'rescue medications', using a protocol successfully implemented, but rarely required, in previous studies by the investigators.²⁰
 - Allowable 'rescue medications' will be identical to first- and second-line medications detailed in the medical care protocol. In addition, weak opioids (e.g. Tramadol) may be used in select cases. Decisions regarding 'rescue medication' selection will be made collaboratively between the provider and patient after a discussion of risk/benefit profiles and preferences.
- Treating clinicians, in consultation with the PIs, may refer for specialty care in the case of AEs or chronic BRLP complications that cannot be adequately managed with the assigned intervention (e.g., progressive neurological deficits).
- Participants will be encouraged to seek any required care for conditions unrelated to the study.

5.3.3. Prohibited Interventions

Participants will be asked to limit treatment to their assigned intervention for the length of the initial 12-week intervention period. However, participants retain the right to discontinue study treatment at any time. Providers will be taught to refrain from delivering interventions that fall outside the scope of the study protocols (see above).

5.4. Adherence Assessment

The total number of treatments will be decided by the treating clinician based on each individual participant's clinical presentation and response to care, as is done in clinical practice. We anticipate 6-10 visits being prescribed for most participants receiving SSM and 2-4 visits for most participants receiving medical care. Participant adherence to assigned interventions will be documented at each visit in the clinical notes.

Treatment adherence is defined as:

- Attending 2 or more Medical Care sessions or 6 or more SSM sessions
And
- Not dropping out of active treatment

5.5. Intervention Fidelity

We will apply robust fidelity activities based on our experience from previous studies to facilitate future intervention replication, internal validity, and accurate interpretation of outcomes.⁹⁶⁻⁹⁸ This includes training and certification (described in section 5.1); use of standardized intervention checklists to guide clinicians through each session; and monthly group meetings with key investigators to receive ongoing coaching in intervention protocols.⁹⁹

Fidelity assessments. All intervention visits will be video recorded with patient consent; a random selection of 10% will be reviewed for fidelity by study investigators. Standardized fidelity instruments will be used to document required, allowed, and prohibited intervention activities and elements. Individualized feedback will be provided to providers as needed based on fidelity assessments.^{99,100} Additionally, standardized treatment clinical report forms will be reviewed for required, allowed, and prohibited interventions.

6. STUDY PROCEDURES

Participation in the pilot study is expected to last approximately 7 months (from initial screening to month 6 follow up assessment). Participants will be sent their final evaluation (a self-report survey) six months after randomization.

6.1. Schedule of Evaluations

(See next page)

Table 5. Pilot Study Data Collection Schedule

Assessment	Initial Screening	Baseline 1	Baseline 2/ Enrollment (Day 0)	Intervention Visits (Month 0-6)	Weekly Follow-Up (Week 1-26)	Monthly Follow-Up (Month 1-6)	Follow-Up (Month 2)	Follow-Up (Month 3)	Follow-Up (Month 6)
Informed Consent	x	x	x						
Demographics	x	x							
Clinical History	x	x							
Physical Exam		x							
Inclusion/Exclusion Criteria	x	x	x						
Quebec Task Force Classification		x							
STarTBack Screening Tool Status		x							
BRLP & LBP frequency & intensity		x	x		x				
Disability, PROMIS-29+2		x	x			x			
Productivity loss, Medication use, Healthcare use			x			x			
Social emotional support, Domain-specific life satisfaction, Perceived stress, Chronic pain acceptance, Chronic pain coping behaviors, Physical activity level, Self-efficacy, Fear-avoidance beliefs, Pain catastrophizing			x					x	x
Treatment expectations			x				x		
Overall satisfaction, Use of key SSM skills, and Global improvement								x	x
Patient-provider connection, healthcare environment							x	x	
Satisfaction with specific components of SBSM								x	
Treatment administered				x					
Adverse events*				x		x			
Qualitative Measures			x					x	
Study close out									x

*Participants can also report adverse events to the PI's or study staff at any point during the trial. **Qualitative data will also be collected from providers regarding their views of barriers and facilitators to care; additionally, as part of supplemental aims, qualitative data will be collected from other stakeholders not taking part in the pilot study to assess their views.

6.2. Description of Evaluations

6.2.1. Pilot Study Screening Evaluations

Consenting Procedures

Potential participants will consent at 4 different time points: a brief initial online screen, a phone screen with study staff, and at two baseline screening appointments.

Initial screening (Online/Phone)

- Interested individuals will be initially screened by a web-based screening portal. An overview of the study will be provided during the web-screen, and electronic consent secured prior to collecting preliminary information on eligibility (e.g. age, English literacy, BRLP severity)
- Following the web-based screening, potential participants will undergo a phone interview with study staff to confirm inclusion criteria (e.g. age, duration and severity of BRLP) and the lack of easily identifiable exclusion criteria (e.g. history of spinal fusion). Verbal consent to collect this information will be collected at the initiation of the phone interview.

Baseline Screening Appointments

- Potential participants will be given a hard or electronic consent form to review on their own that will describe the screening and study procedures at the first baseline screening appointment. See Section 11 for a full description of the consent form. They will be given ample time to review the form on their own and ask questions.
- The Principal Investigators, research coordinator, or designee (i.e., research staff, an investigator) will review the consent form, section by section, one-on-one with each potential participant during the consent interview; participants will be invited to ask questions as they proceed through each section.
- Easy to understand, IRB pre-approved, electronic and print informational materials, including visual media, will be used to facilitate understanding.
- A signed and dated consent form will be obtained from each study candidate. All participants will be given a copy of the signed consent form for their personal records.
- Original signed paper consent forms will be secured in the respective participants research file at the UMN. Signed e-consent forms will be maintained in REDCap.
- Only individuals who demonstrate comprehension will be considered eligible to participate. Persons who are not able to read and write in English or consent for themselves are ineligible.
- At the second baseline appointment, participants will confirm continued consent for the study prior to randomization.

Consent & Human Subjects Training

All research staff obtaining informed consent are required to undergo project specific human subjects training that addresses the essential components to the informed consent process. See Section 11 for additional information about the consent form. In addition,

staff will complete human subjects training in accordance with the UMN's human subjects and HIPAA training requirements.

Changes to the Informed Consent Form

In the event the informed consent form changes, following necessary IRB approvals, study staff will meet with the PI or designee and review changes to the form prior to conducting consent with a potential participant. See the Participants Rights and Confidentiality section for additional information.

If potential participants need to be informed of specific changes in the risks or benefits of study participation, an addendum consent will be used. This addendum will be used to inform enrolled participants about significant new findings that may have a bearing on their willingness to continue participation in the study. The addendum consent will be given to the participant at a study visit or mailed to the participant's home.

Screening Procedures

Initial Screening (Online/Phone)

- Following consent, potential participants will be asked a series of self-report questions through an online portal to screen basic eligibility. Persons who meet basic inclusion criteria (e.g., age, BRLP intensity of 3 or higher, English literacy) and who otherwise have no obvious exclusions (e.g., pregnancy, history of surgical fusion of lumbar spine) will be contacted by study staff, who will ask specific health-related, questions pertaining to inclusion (e.g., LBP episode duration).
- Baseline screening visits (In-person) will occur as soon as possible, but the first baseline screening visit must occur within 30 days of completing the phone screen; otherwise, the phone screen will be redone.

Baseline Screening Visit 1

- Written or electronic consent will be collected from participants prior to any screening procedures at this visit.
- Participants will complete study surveys to collect basic demographic information along with health history information to inform the detailed clinical evaluation and confirm eligibility. The surveys will include:
 - Demographics
 - Limited set of key patient-reported outcomes (see Table 5)
 - Past and ongoing BRLP treatment
 - Comorbid health conditions
 - Participants reporting current or past history of mental health disorders and related treatment will undergo additional screening if unmanaged major depression is suspected or reported. Scores of 3 or higher on the Patient Health Questionnaire-2 (PHQ-2)¹⁴⁷ will lead to additional screening for suicidality. A score of 2 or higher on question 12 from the Quick Inventory of Depressive Symptomatology-Self Report (QIDS-SR)¹⁴⁸ for suicidal ideation will warrant

- exclusion and referral. Mental health resources will be provided to these participants (e.g. suicide hotlines, emergency services)
- Participants reporting potential substance abuse (having 6 or more drinks on a weekly basis, using illegal drugs, or prescription medication for non-medical reasons) will undergo additional screening for potential substance abuse. Scores ≥ 20 on the 10-item Alcohol Use Disorders Identification Test (AUDIT) for alcohol¹⁴⁹ or ≥ 6 on the 10-item Drug Abuse Screening Test (DAST)¹⁵⁰⁻¹⁵² are exclusionary and warrant referral. The AUDIT and DAST will be available to administer at any time if the clinician suspects a problem.
- A licensed healthcare provider (e.g., DC, PT, advanced practice nurse) will conduct a clinical history and a focused low back and lower extremity physical exam that will include posture assessment, orthopaedic and neurological tests (e.g. straight leg raise, lower extremity muscle strength, sensation, and reflexes), palpation, and vascular assessments. Current medications and vitals will also be collected.
- Women with reproductive potential will take a pregnancy test.
- Suspicion of declining cognitive function during medical history/clinical exam will lead to administration of the Mini-mental state examination. A score of 23 or below is exclusionary.¹⁵³
- Eligible participants will complete baseline measures of self-reported study outcomes (see Table 5).

Baseline Screening Visit 2 (within 21 days of Baseline Screening Visit 1)

- Prior to the second baseline screening visit, investigators and study clinicians will review each case at weekly case review meetings for clinical eligibility determination. A review of inclusion and exclusion criteria based on the medical history, physical exam, and patient reported measures collected at the first baseline screening visit will be conducted for each participant. The review committee reaches consensus on every case and recommends exclusion, inclusion, or further evaluation to determine eligibility (e.g. diagnostic imaging).
- Potential participants who present with signs and symptoms suggestive of a specific cause of BRLP (e.g., nephrolithiasis, cauda equina), contraindication to study treatments, (e.g., inflammatory arthropathies of the lower back), or other condition that warrants medical attention will be referred to their medical provider for follow-up and management.
- Eligible participants will complete repeat assessments of key patient reported outcomes to confirm eligibility (i.e. BRLP intensity) and account for potential regression to the mean (See Table 5). Baseline measures of other self-reported study outcomes (clinical, behavioral, and mediating outcomes) will also be completed.
- In addition, participants will provide feedback on key study recruitment and screening procedures using open-ended survey questions.
- Confirmation of consent and randomization of eligible participants will occur at the second baseline screening visit.

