1.2. Aim Two

To assess feasibility of the SUPPORT trial through achievement of pre-specified targets for:

- a. Recruiting and enrolling individuals with chronic BRLP by assessing recruitment rates (screens/month; % women and minorities); enrollment rates (participants/month; % women and minorities); and screened participants' views and perspectives (identification of barriers and facilitators for research participation)
- b. Delivering experimental and comparison interventions by assessing acceptability and adherence (% never receiving treatment; % receiving prohibited treatments during intervention phase); % attending required sessions; % participating in home practice and taking medications as directed; % satisfied with treatment); provider intervention fidelity rates (% of required activities delivered) and participant and provider views (barriers and facilitators to engaging in/providing interventions; views regarding affordability, practicality, effectiveness, acceptability, and equity)
- c. Data collection by assessing follow up rates of future clinical trial outcome measures (% of complete assessments at 12 weeks and six months, in addition to % of completed weekly pain surveys)

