- Healthcare use for BRLP including MRIs, injections, hospitalizations, surgeries, and provider-based visits.²⁰
- Physical activity levels (e.g. amount of sedentary activity) measured with the International Physical Activity Questionnaire.¹²⁹

Mediating Outcomes

Mediating outcomes and targets of the intervention theorized to affect the clinical and behavioral outcomes will also be collected to inform protocol refinement. These include:

- BRLP related capabilities (e.g. knowledge, skills, physical capacity), opportunities (e.g. available resources), motivations (e.g. optimism)⁵¹⁻⁵³ for participants enrolled into supported self-management.
- Beliefs related to self-efficacy as measured by confidence in ability to manage daily activities, symptoms, emotions, and social interactions (PROMIS self-efficacy for managing chronic conditions);¹³⁰ the chronic pain acceptance questionnaire will also be administered.¹⁵⁷
- Fear-avoidance beliefs using the Fear-avoidance Beliefs Questionnaire¹³¹
- Catastrophizing measured using the 13-item Pain Catastrophizing Scale;¹³² it uses a 5-item point scale (0=not at all, 4 all the time) and has internal consistency and validity.
- Expectations about back pain treatments (HEAL items).¹³⁵

Qualitative measures

Qualitative measures will be collected from enrolled subjects, as well as providers regarding their views of barriers, facilitators, affordability, practicality, effectiveness, acceptability, and equity.

As part of the supplemental aims, qualitative information will be collected from other stakeholders with pain who are underrepresented in CIH LBP/BRLP research to explore their views of barriers and facilitators to care for LBP/BRLP.

Randomization

In the pilot study, randomization precedes intervention administration. Randomization will occur within 21 days of completing the first baseline screening visit. Participants who are not randomized within this time frame will repeat the in-person screening. Interventions will be initiated within 14 days of randomization/enrollment.

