9.4. Outcomes

9.4.1. Primary Outcomes

Primary outcomes for the pilot study are feasibility measures for the larger randomized trial including:

- Recruitment feasibility - Number of participants screened per month; percentage of screened participants who are female; percentage of screened participants who are minorities; participant views and perspectives on research participation
- Enrollment feasibility - Number of participants enrolled per month; percentage of enrolled participants who are female; percentage of enrolled participants who are minorities; participant views and perspectives on research participation
- Intervention acceptability and credibility feasibility - Percentage of enrollees not receiving any treatment; percentage of enrollees receiving prohibited treatments during the 12-week intervention phase (contamination); percentage of enrollees satisfied with treatment

- Participant treatment adherence feasibility - Percentage of enrollees attending required sessions; percentage of enrollees in the supported biopsychosocial self-management group reporting participation in home practice; percentage of enrollees in medical care group reporting taking medications as prescribed
- Provider fidelity feasibility - Percentage of provider visits where 100% of required intervention activities were delivered
- Data collection feasibility - Percentage of enrollees completing the month 3 assessment; percentage of enrollees completing the month 6 assessment; percentage of weekly pain severity and frequency assessments completed

Table 6. Feasibility Measures & Targets

Recruitment	≥40 screened/month (50% women, 25% minorities)
Enrollment	≥8 enrolled/month (50% women, 25% minorities)
Intervention acceptability, credibility	≤10% never receive any treatment; ≤10% receive prohibited treatments during 12-week intervention phase (contamination) ≥80% satisfied with treatment
Participant adherence	≥80% participants attend required sessions (SSM=4; MC=2) ≥70% of SSM participants report participation in home practices ≥70% of MC participants report taking medications as prescribed
Provider fidelity	Providers deliver 100% of required intervention activities on ≥70% of visits
Data collection	≥85% of participants complete 12 weeks follow up ≥80% of participants complete 25-week follow up ≥80% of weekly pain severity and frequency surveys completed

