13. STUDY TIMELINE

Planning phase. This project has a 6 month planning phase during which time the study team will develop and obtain the necessary regulatory approvals for the protocol, the Study Accrual and Retention Plan (SARP), Data Safety and Monitoring Plan (DSMP) if required, and case report forms (CRFs). Qualitative data collection will also be conducted with physical therapists (PT) and doctors of chiropractic (DCs) to inform development and refinement of the supported self-management (SSM) intervention. Qualitative data will also be collected from community members to provide feedback on patient-facing materials. Training of providers will also take place prior to commencing the pilot study clinical phase.

Clinical phase. This pilot study will take place over the course of one year (last 6 months of year 1, and first 6 months of year 2). We project enrolling 40-50 participants over a 6 month period.

Data collection & analyses. Data collection will begin from the first screening, through the 6 month follow up (quarter 3 of year 2). Data preparation and analyses will take place in the final 2 quarters of year 2.

	Year One				Year Two			
	Q1	Q2	Q3	Q4	Q1	Q2	Q3	Q4
Planning								
IRB Approval	X							
Protocol, SARP, DSMP, CRF Approval	X	X						
MOP Development		X	X					
Training		X	X					
Qualitative data collection and analyses (Providers, patient representatives, other stakeholders)	X	X	X	X	X	X	X	
Clinical								
Recruitment			X	X	X			
Screening & Enrollment				X	X			
Intervention Application				X	X	X		
Fidelity Monitoring				X	X	X		
Data Collection & Analysis (Pilot Study & Supplemental Aims)								
Data Collection			X	X	X	X	X	
Data Preparation & Analysis							X	X
Dissemination								X
Preparation of proposal for phase II trial								X

Enrollment of First Subject

First enrolled subject anticipated in the last quarter of Year 1.

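### Aim 2a promises the views of screened people on barriers and facilitators to research participation, but open-ended feedback is collected only from those who reach Baseline Screening Visit 2

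*Combined protocol and SAP*

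**What the plan says.** Section 1.2, Aim Two (a), includes "screened participants' views and perspectives (identification of barriers and facilitators for research participation" among the things to be assessed, and Section 9.1 repeats the commitment in shorter form. Section 9.4.1 carries it into the primary outcomes, listing "participant views and perspectives on research participation" under both recruitment and enrollment feasibility, without saying whose views are meant.

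On collection, Section 6.2.1 places the recruitment and screening feedback at Baseline Screening Visit 2: "In addition, participants will provide feedback on key study recruitment and screening procedures using open-ended survey questions". Table 5 (Section 6.1) marks Qualitative Measures at Baseline 2/Enrollment and Month 3 and leaves the Initial Screening and Baseline 1 columns blank. Section 6.2.2 adds: "Qualitative measures will be collected from enrolled subjects, as well as providers".

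For people who do not get that far, Section 4.3 keeps a list of every screened candidate with the reason for ineligibility or non-participation. Section 9.4.2 and Table 7 report the percentage declining and the main reasons as protocol refinement measures.

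**The concern.** The population named in the aim and the population that can answer are different. To reach the survey a person must pass the web screen, the phone screen, Baseline 1 and the case review, and then come back. The feedback on barriers therefore comes only from people whom those barriers did not stop before that point.

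Section 9.5 says coded themes will be scored present or absent for each case and reported as frequencies. With the collection point as planned, each frequency is conditional on reaching Baseline 2. A barrier that acts mainly earlier, such as visit burden or mistrust, could appear rare because the people it removed are not in the denominator. A primary qualitative outcome would then answer a narrower question than the aim poses, with nothing in the report to show it.

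**Working it through.** **Inputs**
- Screening target, Table 6: "≥40 screened/month (50% women, 25% minorities".
- Enrollment target, Table 6: "≥8 enrolled/month (50% women, 25% minorities".
- Planned enrollment, Section 13: "We project enrolling 40-50 participants over a 6 month period". The Section 13 chart also shows screening and enrollment over two quarters, that is, six months.
- Number attending Baseline 2: not given in the documents.

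**Step 1. Reproduce the plan's enrollment figure.** 8 per month × 6 months = 48, which lies inside the planned 40 to 50. The monthly target and the timeline agree.

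**Step 2. Share of screened people not enrolled.** Screened: 40 × 6 = 240. Share not enrolled = 1 − enrolled/screened.
- 48 enrolled: (240 − 48)/240 = 192/240 = 80.0%
- 40 enrolled: 200/240 = 83.3%
- 50 enrolled: 190/240 = 79.2%

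If screening at the minimum rate ran through all three quarters shown for recruitment (40 × 9 = 360 screened), 40 to 50 enrolled would give 320/360 = 88.9% to 310/360 = 86.1%. Both targets are minimums, so the real ratio may differ either way.

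**Step 3. Share not reaching the survey.** Section 6.2.1 lists the feedback before confirmation of consent and randomization at the same visit, so some respondents may not be enrolled. Let f be the fraction of Baseline 2 attendees who are not randomized (an assumption). Attendees = 48/(1 − f), and the share not reaching the survey = 1 − attendees/240.

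| f (assumed) | Attendees | Not reaching Baseline 2 |
|---|---|---|
| 0 | 48 | 80.0% |
| 10% | 53 | 77.8% |
| 20% | 60 | 75.0% |
| 30% | 69 | 71.4% |
| 50% | 96 | 60.0% |

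**Step 4. What this does to a theme frequency.** For any barrier, the frequency among all screened is w × (frequency among Baseline 2 attendees) + (1 − w) × (frequency among those who leave earlier), where w is the share reaching Baseline 2. At target rates with f from 0 to 30%, w is about 20% to 29%. The plan observes only the first frequency. The second has most of the weight, and no open-ended data inform it.

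**The case against.** The case for leaving the plan alone has several sound parts.

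- **Early leavers are not ignored.** A reader might infer that they are never asked anything. Section 4.3 logs reasons for every screened candidate, and Section 9.4.2 reports the main reasons for declining. A stated reason for declining is barrier information. This stands, and it limits the gap to open-ended views. The documents do not say how reasons are elicited, do not seek facilitators from these people, and do not say that those who simply fail to return are contacted.
- **The survey is not confined to enrollees.** A reader might take the Section 6.2.2 sentence to restrict it to them. That sentence goes on to list intervention topics such as affordability and practicality, which match Aim 2b, while the Section 6.2.1 survey precedes randomization. This stands.
- **Ineligible is not deterred.** Sections 4.1 and 4.2 contain many clinical criteria, so part of the 80% leaves for clinical reasons. The documents give no split. Aim 2a nevertheless says screened, without that limit.
- **Little else depends on the survey.** Table 6 sets no target for views, and Section 14 says refinement will use Table 7, whose recruitment and enrollment rows are not restricted to Baseline 2 attendees. This stands, so it would be too strong to say that phase II recruitment as a whole would be designed on a biased picture.
- **Underrepresented groups have dedicated work.** Supplemental Aim 2 covers 20 to 30 additional community members, supported by the Community Advisory Team, and the percentage of minorities is reported at both screening and enrollment. A reader might infer that these groups suffer most from the gap; the documents do not show that. The interviews are nevertheless an additional sample, not defined as people who went through this trial's screening, and so do not replace the views of its screenees.

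**Conclusion.** The mismatch is real but moderate. The plan commits to screened people's views on barriers and facilitators, yet collects open-ended views only from those who attend Baseline 2. For the rest it holds a reason for ineligibility or non-participation.

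On size, 80% (79% to 83%) is the share not enrolled, derived from two minimum targets over six months. It should not be read as the share that misses the survey, which the documents do not give. That share is about 71% to 78% if 10% to 30% of Baseline 2 attendees are not randomized, and still 60% at 50%. It mixes ineligible and deterred people in unknown proportions. Under each of these assumptions most of the population named in Aim 2a has no route to give open-ended views. No feasibility threshold is affected; what is affected is the interpretation of one primary qualitative outcome.

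**What to change.** 1. In Section 6.2.1 and Table 5, add a short optional open-ended item on barriers and facilitators at the end of the web screen and of the phone screen. Send the same item by emailed link to those who decline, are excluded or do not return after Baseline 1.
2. In Section 9.5, report themes separately for enrollees and for screened people who were not enrolled, and split the latter into ineligible and declined or not returned. Present them beside the logged decline reasons, with the response rate for each group.
3. If this is not done, restate the views outcome in Sections 1.2, 9.1 and 9.4.1 as covering Baseline 2 attendees only.

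Consent is already obtained at the web and phone screens (Section 6.2.1), and both already use electronic data entry (Section 10.1), so no new visits or staff are needed. The cost is a small amendment and some extra coding. The main drawback is that response among people who leave early will probably be low and self-selected, which is why the response rate must be shown with the themes. Option 3 costs almost nothing, but it gives up the broader question.
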